2.7 Safety endpoints

Safety endpoints include the following:

At 75 ± 5 days following each transplant, at 365 ± 14 days following the first and last islet transplant(s), at 730 ± 14 days following the last islet transplant, and at 1095 ± 14 days following the last islet transplant:

- The incidence and severity of adverse events (AEs) related to the islet transplant procedure, including: bleeding (>2 g/dL decrease in hemoglobin concentration); segmental portal vein thrombosis; biliary puncture; wound complication (infection or subsequent hernia); and increased transaminase levels >5 times upper limit of normal (ULN)
- The incidence and severity of AEs related to the immunosuppression including: allergy; reduction in glomerular filtration rate (GFR); increase in urinary albumin excretion; addition or intensification of anti-hypertensive therapy; addition or intensification of anti-hyperlipidemic therapy; oral ulcers; lower extremity edema; gastrointestinal toxicity; neutropenia, anemia, or thrombocytopenia; viral, bacterial, or fungal infections; and benign or malignant neoplasms
- The incidence of change in the immunosuppression drug regimen
- The incidence of immune sensitization defined by presence of anti-HLA (histocompatibility antigen) antibodies absent prior to transplantation
- The proportion of subjects who withdraw from study treatment due to an organ transplant

At 365 ± 14 days following the first and last islet transplant and at 1095 days following the last islet transplant:

- The incidence of worsening retinopathy as assessed by change in retinal photography

3. Subgroup Analysis

A Subject may enter the study because she/he is having severe hypoglycemic events that require assistance or because she/he is unable to reduce HbA1c level to below 7.5% on Intensive Insulin

Statistical Analysis Plan

Therapy (see inclusion criterion 7 in the protocol). The latter group may be very small. However, if there are at least 6 subjects in each group, we will perform subgroup analyses that examine these two subgroups separately. Analyses will include all primary and secondary outcome measures and use the same analysis strategies that were used for those measures. Please note that power for these analyses will be very small but the results may lead to a better understanding of the mechanisms of outcome.

4. Sample Size and Power Calculations

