5.1.1 Study Period

The trial consists of three periods: (1) the pre-transplant period, which includes screening, enrollment, and wait list time; (2) the period that includes the islet transplant procedure(s); and (3) follow-up visits through 24 months following the last transplant. The study period of this trial is a 36-month follow-up after the final islet transplant. Subjects may undergo up to 3 transplants in the course of this study; the last transplant can occur not later than 8 months following the first transplant.

In the first period, individuals who meet the general inclusion criteria will be approached regarding participation in the study. After informed consent has been obtained, they will be formally enrolled into the study. Eligibility will be confirmed based on the results of the screening visit procedure detailed in Appendix 1 of the CIT-06 protocol. Enrolled subjects who meet the eligibility screening for the studies will be put on the waiting list for an islet transplant.

After completion of the screening assessments confirming eligibility for the study, a subject will undergo 12 months of intensive insulin therapy (IIT) by an experienced diabetologist (see Appendix 3). If a subject received at least 12 months of **intensive diabetes management** prior to enrollment and experienced at least one episode of **severe hypoglycemia** during that time, the subject would not be required to receive IIT while on study as long as they have a Clarke score of 4 or more. A subject is required to return to the study site for clinic visits every 3 months while undergoing IIT and while on the waitlist. Monthly HbA1c sampling between the required 3 month interval visits may be drawn locally, sent from the local lab to the study site and then shipped to the central lab for testing. Eligibility will be reconfirmed after 4 months of IIT and after 12 months of IIT. All eligibility assessments must be within the windows required for initial study enrollment. Once eligibility has been reconfirmed, a subject will be placed on the **wait list**. The subject will continue IIT while on the **wait list**.

Once a compatible islet preparation becomes available, a subject's eligibility will be re-confirmed and eligible subjects will begin immunosuppression therapy on Day -2 (Day 0 is defined as the day of transplant).

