8.2 Analysis of binary outcome variables

Binary outcome variables will be displayed as percents with 95% exact confidence intervals (Rosner, 1995). The exact confidence interval (P_L, P_U) will be as the solutions to the following equations. If x is the observed outcome (that is, there are x successes in the 24 subjects) then the lower bound will be the solution P_L to the equation

$$0.025 = \Pr \{ \text{at least } x \text{ successes} \mid \text{probability of success} = p_L \} = \sum_{k=x}^{24} \binom{24}{k} p_L^k (1-p_L)^{24-k}.$$

The upper bound will be the solution to the equation

$$0.025 = \Pr \{ \text{no more than } x \text{ successes} \mid \text{probability of success} = p_U \} = \sum_{k=0}^x \binom{24}{x} p_U^k (1 - p_U)^{24-k}.$$

Standard search methods will be used to solve these equations.

8.3 *Analysis of time to event measures*

All time to event measures will be summarized using Kaplan-Meier (product limit) life table methods. Results will be displayed as survival plots. Tables with estimates and 95% confidence intervals for the rates at 1-year, 2-years, and 3-years after the first and last islet transplants will be provided. Separate analyses will be performed for time from first transplant and time from last transplant.

9. Analysis of Demographic and Baseline Measures

9.1 *Baseline Data*

Baseline data collected for the ITT analysis consists of demographic information and medical/physical assessments during the waiting period for islet transplant. These data will be grouped into the following categories:

- Demographic variables
 - Age
 - Sex
 - Race (White, Black, Hispanic, Asian and Other)
- Body Habitus and Quality of Life
 - Body Weight
 - Height
 - Body Mass Index (BMI)
- Diabetes Control
 - Insulin requirement (units/day)
 - HbA1c
 - Fasting and post prandial plasma glucose
 - Fasting and post prandial C-peptide
 - 90-minute C-peptide following consumption of Boost[®] or equivalent
 - 90-minute glucose following consumption of Boost[®] or equivalent
 - Number of severe hypoglycemic events in the last year
 - MAGE score
 - LI
 - Clarke Score
 - HYPO score
 - β -score
 - C-peptide/(glucose·creatinine) ratio

Statistical Analysis Plan

- Measures of Cardiovascular function
 - Carotid intimal thickness
 - Atherogenic profile (fasting lipids, c-reactive protein, serum amyloid A, Apolipoprotein A1, Apolipoprotein B, and the ratio of Apolipoprotein A1 and Apolipoprotein B).
- Measures of Renal function
 - Serum Creatinine

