14.2 Analysis of Safety Endpoints

The safety secondary endpoints in this study target AEs related to islet transplantation (transplant procedure and/or islet product) and the immunosuppression and/or infection prophylaxis.

The targeted AEs related to the islet transplantation include:

AE-IIP-1: Bleeding (>2 g/dL decrease in hemoglobin concentration)

AE-IIP-2: Segmental portal vein thrombosis

AE-IIP-3: Biliary puncture

AE-IIP-4: Wound complication (infection or subsequent hernia)

Statistical Analysis Plan

AE-IIP-5: Increased transaminase levels (>5 times ULN)

The targeted AEs related to the immunosuppression and infection prophylaxis therapy include:

AE-IP-1: Allergy

AE-IP-2: Reduction in GFR

AE-IP-3: Increase in urinary albumin excretion

AE-IP-4: Addition or intensification of anti-hypertensive therapy

AE-IP-5: Addition or intensification of anti-hyperlipidemic therapy

AE-IP-6: Oral ulcers

AE-IP-7: Lower extremity edema

AE-IP-8: Gastrointestinal toxicity

AE-IP-9: Neutropenia, Anemia, or Thrombocytopenia

AE-IP-10: Viral, Bacterial, or Fungal Infections

AE-IP-11: Benign or Malignant Neoplasms

Results will be reported for the following time points: 75 days and one year after the first and last transplant and at 2 years, and 3 years after the first and after the last islet transplant.

We will report incidence of each AEs categorized by MedDRA term and body system. Tables with relation to the islet product and to the immunosuppression will be reported. For each category, the number of resolved events will be reported. The mean, median, standard deviation and range for the number of days until the AE is resolved will also be reported. Results will be summarized using the template provided in Appendix 2.

The incidence rate of immune sensitization, defined as detection of anti-HLA antibodies at 75 ± 5 days following the first and last islet transplant and at and one year after the first and last transplant and at 2 years, and 3 years after the first and after the last islet transplants. Exact two-sided 95% confidence interval of the incidence rate will also be reported.

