14.2.1 Statistical Analyses of Adverse Events

AEs will be analyzed according to the body system described in the *CIT-TCAE* manual. Any event that appears in a body system will be categorized into one of the five severity grades according to the *CIT-TCAE* manual or the general definition of severity given in Table 7 and analyzed accordingly. For each event, we will analyze its incidence rate per 100 person-days. Suppose for each subject, the incidence of a particular event is a Poisson process with the homogeneous incidence rate λ . At the time of analysis, if a subject is only followed r days after the initiation of induction immunosuppression, the incidence of this event is distributed according to the Poisson distribution with mean $r\lambda/100$. The maximum likelihood estimate of the

Statistical Analysis Plan

incidence rate will be obtained based on data collected from the available subjects at the analysis time. The 95% confidence interval derived using the maximum likelihood estimator theory will be also reported. The results will be summarized in the table provided in SAP Appendix 4. Moreover, we will also list all the individuals who have ever had an incident of any of the AEs listed in Appendix 5 since their initiation of induction immunosuppression.

15. Interim Analyses and Safety Monitoring Analyses

The DSMB will be convened to review safety and efficacy data following National Institutes of Health (NIH) policy. When requested, formal interim analyses to assess safety and efficacy will be performed. Formal interim analyses will include distributions of endpoints, biomarkers and AEs. Additional analyses may be requested by the DSMB.

15.1 *Interim Analysis for Early Stopping*

We will use the method for interim analyses described by Emerson and Fleming (Emerson & Fleming, 1989) which is implemented in the SPlus module S+SeqTrial (TIBCO_Software, 2009) to provide cut-points for an interim analysis for futility. This module does not require specifying the timing of interim analyses and controls the overall type I and type II errors. In order to make what follows clearer we provide some notation. Let p represent the true probability of a favorable outcome in islet transplanted subjects.

The efficacy hypothesis is

$$H_{01} : p \leq 0.27 \text{ versus } H_{a1} : p > 0.27.$$

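### Days to adverse-event resolution are summarised with no censoring of ongoing events and no stated cut-off, so reported durations of persistent harms are biased short

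*SAP*

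**What the plan says.** SAP section 14.2 lists 16 targeted AEs: 5 related to the islet transplantation and 11 to immunosuppression and infection prophylaxis. On duration it makes two commitments. One concerns how long events last: "The mean, median, standard deviation and range for the number of days until the AE is resolved will also be reported". The other is a count that stands beside it: "For each category, the number of resolved events will be reported".

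The reporting times are set earlier in the same section: "Results will be reported for the following time points: 75 days and one year after the first and last transplant", followed by two and three years after the first and last transplant. The layout is then fixed: "Results will be summarized using the template provided in Appendix 2".

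For every targeted AE and each of five severity grades plus a Total column, Appendix 2 gives a total number and percentage. A Resolved entry follows with its own number and percentage, and directly beneath it stand mean, s.d., median and min-max. There is no line for events still ongoing.

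Elsewhere, section 8.3 sets a general rule: "All time to event measures will be summarized using Kaplan-Meier (product limit) life table methods". AE resolution is not among the time-to-event outcomes listed in sections 2.6 and 12.4, and section 14.2 does not refer to 8.3. Section 14.2.1 mentions a data cut, but only for AE rates: the "incidence rate will be obtained based on data collected from the available subjects at the analysis time".

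**The concern.** Time from onset to resolution is a time-to-event quantity, and some events will not have resolved when the table is made. A plain mean or median of days to resolution has no place for them. The events left out are the long-lasting ones, so the remaining durations are systematically shorter than the true ones.

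Several targeted AEs may persist: reduction in GFR (AE-IP-2), increased urinary albumin excretion (AE-IP-3) and neoplasms (AE-IP-11). The subjects are kidney-transplant recipients, and section 14 itself stresses the clinical importance of the renal and immunosuppression variables. A reader who takes the median in Appendix 2 as the typical duration of such a harm would be misled. Addition or intensification of anti-hypertensive or anti-hyperlipidemic therapy (AE-IP-4, AE-IP-5) raises a further problem: the SAP does not say what resolution of such an event means.

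**Working it through.** The SAP states no AE duration or resolution rate, so there is no figure to reproduce. The direction follows from the definition. The sizes below are illustrations under stated assumptions.

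**Inputs from the SAP.** Reporting times are 75 days and 1, 2 and 3 years (14.2). Section 2.7 sets the first window: "At 75 ± 5 days following each transplant". Section 5.1.1 sets the start of therapy: "eligible subjects will begin immunosuppression therapy on Day -2".

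**Assumptions, not in the SAP.** Duration D is exponential with true mean m. Onset is at day 0. Resolution dates are cut at day T.

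**Formulas.**
- Share resolved: p = 1 − exp(−T/m)
- Mean among resolved events: m − T·exp(−T/m)/p
- Median among resolved events: −m·ln(1 − p/2)
- True median: m·ln 2

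**Worked case, m = 90, T = 75.** exp(−75/90) = 0.4346, so p = 0.565. Resolved-only mean = 90 − 75 × 0.4346/0.5654 = 32.3 days. Resolved-only median = −90 × ln(1 − 0.2827) = 29.9 days. The true median is 90 × 0.693 = 62.4 days.

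| True mean (d) | Cut T (d) | Resolved | Resolved-only mean (d) | Resolved-only median (d) | True median (d) |
|---|---|---|---|---|---|
| 30 | 75 | 92% | 23.3 | 18.4 | 20.8 |
| 90 | 75 | 57% | 32.3 | 29.9 | 62.4 |
| 365 | 75 | 19% | 36.2 | 35.6 | 253 |
| 365 | 365 | 63% | 152.6 | 138.7 | 253 |
| 365 | 1095 | 95% | 307.6 | 235.3 | 253 |

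With m = 10 and T = 75 the resolved-only mean is almost exactly 10 days, so short, early events are hardly affected.

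**Does censoring repair it?** Simulation of the day-75 cases (200,000 events each) with open events censored gave Kaplan-Meier medians of 20.8 days for m = 30 and 62.3 days for m = 90, matching the true values. For m = 365 the median was not reached, which is the honest answer at that cut.

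**Permanent events.** If half the events never resolve and the rest last 20 days on average, the resolved-only mean is 18 to 20 days at every cut, while the Kaplan-Meier median is not reached. Longer follow-up does not remove this bias.

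**Dependence on the cut.** Take events arising uniformly over days 0 to 75.

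| True median (d) | Dates cut at day 75 | Dates followed to day 1095 |
|---|---|---|
| 90 | 24% resolved, median 19 d | about 100% resolved, median 90 d |
| 365 | 7% resolved, median 21 d | 87% resolved, median 299 d |

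The same planned table can therefore differ greatly according to a cut-off that the SAP does not state. If dates were cut at the day-75 visit, the longest possible duration for an event arising on protocol therapy would be 75 days from transplant, 75 + 2 = 77 from the start of immunosuppression, and 75 + 5 + 2 = 82 at the end of the window.

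**The case against.** The strongest reply has four parts.

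1. **Ongoing harms remain visible.** Appendix 2 prints the total number directly above the number resolved, by grade, so the unresolved count follows by subtraction. This stands: events drop out of the duration statistics, not out of the report. It does not correct the mean or median printed beneath.

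2. **No cut at day 75 is stated.** A reader might infer that durations in the day-75 report cannot exceed about 75 days. The SAP does not support that as a fact. Section 14.2 names times for which results are reported, not a truncation of resolution dates. Section 14 says that summaries for the data safety monitoring board (DSMB) use all AE data available at the meeting, and that identical summaries enter the final report. Events arising by day 75 could then carry much later resolution dates, and the second table shows the bias largely or wholly gone in that reading. It remains for late-onset and permanent events. The missing cut-off is itself part of the problem.

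3. **Section 8.3 might already require Kaplan-Meier.** Restricting the statistics to resolved events is an inference from the wording and the template, not an explicit rule. But if 8.3 governs, 14.2 and Appendix 2 contradict it; if it does not, ongoing events have no rule. The text needs correcting either way.

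4. **Little depends on this row.** A reader might infer that the trial's risk-benefit case rests on these durations. It does not. Renal allograft survival, serum creatinine and albumin/creatinine ratio, Kaplan-Meier analysis of renal failure, longitudinal creatinine models and AE rates per 100 person-days also cover persistent harm.

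A further practical point stands: with 24 subjects and 16 AEs by five grades, a Kaplan-Meier median in each cell would be unworkable, and repeated events within a subject are not independent.

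**Conclusion.** The point holds in a limited form. As written, section 14.2 and Appendix 2 condition the duration statistics on resolution and give no cut-off for resolution dates. Mean and median durations are biased short whenever an appreciable share of events is ongoing at the cut, most at early cuts and for persistent harms.

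The size cannot be derived from the SAP. Under exponential durations with onset at day 0, it ranges from negligible (true mean 10 days, cut at day 75) to severe (true mean 365 days shown as 36 at day 75, 153 at one year and 308 at three years). The day-75 figures and any ceiling near 75 days hold only if data are cut at that visit.

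This is a descriptive safety table. No test, stopping rule or decision in the SAP uses the row, and the primary analysis is unaffected. The change is nevertheless worth making, because it is cheap and removes a misleading summary.

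**What to change.** In section 14.2 and the Appendix 2 shell:

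- State the cut-off for resolution dates in each report.
- In the Total column for each targeted AE, add the number ongoing and a Kaplan-Meier median time from onset to resolution, shown as 'not reached' where applicable. Censor ongoing events at the cut-off or last contact, and count death as unresolved.
- Say how repeated events within a subject are handled, for example by using the first event per subject.
- Label any retained mean, SD or range as applying among resolved events only.
- For AE-IP-4 and AE-IP-5, either define resolution for reporting purposes or omit the duration rows.

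The cost is SAP wording and a revised table shell. The onset and resolution dates needed are those the planned summary already requires. The downside is that some medians will read 'not reached' and estimates will be imprecise where events are few. Nothing in clinical management changes.

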14.2.1 Statistical Analyses of Adverse Events

AEs will be analyzed according to the body system described in the *CIT-TCAE* manual. Any event that appears in a body system will be categorized into one of the five severity grades according to the *CIT-TCAE* manual or the general definition of severity given in Table 7 and analyzed accordingly. For each event, we will analyze its incidence rate per 100 person-days. Suppose for each subject, the incidence of a particular event is a Poisson process with the homogeneous incidence rate λ . At the time of analysis, if a subject is only followed r days after the initiation of induction immunosuppression, the incidence of this event is distributed according to the Poisson distribution with mean $r\lambda/100$. The maximum likelihood estimate of the

Statistical Analysis Plan

incidence rate will be obtained based on data collected from the available subjects at the analysis time. The 95% confidence interval derived using the maximum likelihood estimator theory will be also reported. The results will be summarized in the table provided in SAP Appendix 4. Moreover, we will also list all the individuals who have ever had an incident of any of the AEs listed in Appendix 5 since their initiation of induction immunosuppression.

15. Interim Analyses and Safety Monitoring Analyses

The DSMB will be convened to review safety and efficacy data following National Institutes of Health (NIH) policy. When requested, formal interim analyses to assess safety and efficacy will be performed. Formal interim analyses will include distributions of endpoints, biomarkers and AEs. Additional analyses may be requested by the DSMB.

15.1 *Interim Analysis for Early Stopping*

We will use the method for interim analyses described by Emerson and Fleming (Emerson & Fleming, 1989) which is implemented in the SPlus module S+SeqTrial (TIBCO_Software, 2009) to provide cut-points for an interim analysis for futility. This module does not require specifying the timing of interim analyses and controls the overall type I and type II errors. In order to make what follows clearer we provide some notation. Let p represent the true probability of a favorable outcome in islet transplanted subjects.

The efficacy hypothesis is

$$H_{01} : p \leq 0.27 \text{ versus } H_{a1} : p > 0.27.$$

Rejecting this null hypothesis would lead to concluding that the favorable outcome rate is better than 27% in patients who receive an islet transplant. In order to ensure that the study provides the maximum safety information, this study will not be stopped for efficacy.

The futility hypothesis is

$$H_{02} : p \geq 0.67 \text{ versus } H_{a2} : p < 0.67.$$

Rejecting this hypothesis would lead to concluding that the favorable outcome rate in patients who receive an islet transplant is not greater than 0.27. The value 0.67 guarantees that the probability of a type II error (accepting the null hypothesis when it is false) is less than or equal to 0.025. That is, the probabilities of type I and type II errors are equal.

In order to illustrate the method, Table 13.1 assumes two equally spaced analyses; an interim analysis when 12 subjects have completed their one-year post first transplant visit and a final analysis when all 24 subjects have completed their one-year post first transplant visit. The table provides cut-points for a recommendation for futility (Reject H_{02}). Column 4 in this table (labeled number of favorable outcomes required) provides the largest number of observed favorable outcomes that would lead to recommending futility.

Statistical Analysis Plan

At the first interim analysis (when 12 subjects have completed the study) the monitoring plan would recommend for futility if no more than 2 of the first 12 islet transplant subjects experienced a favorable outcome at one year after their first transplant.

Table 13.1: Sequential Monitoring Plan

Patients Accrued		Fixed Sample p-value	Number of Favorable outcome Required*
12	Reject H_0	.5000	≤ 2
24	Accept H_0	.0243	<11

Source SPlus SeqTrial

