All Adverse Events	Identification of incidences	Number and percentage of patients who have had the incidence	Identification of incidences	Number and percentage of patients who have had the incidence
Body System A				
Grade 5				
Grade 4				
Event 1	C111 C112 C113* C221 C231 C232 C331 C421 C461	6 (12.5%)		
Event 2				
⋮				
Grade 3				
Event 1				
Event 2				
⋮				
Grade 2				
Event 1				
Event 2				
⋮				
Grade 1				

Statistical Analysis Plan

Event 1 Event 2 ⋮				
Body System B Grade 5 Grade 4 Event 1 Event 2 ⋮ Grade 3 Event 1 Event 2 ⋮ Grade 2 Event 1 Event 2 ⋮ Grade 1 Event 1 Event 2 ⋮				
Body System C Grade 5 Grade 4 Event 1 Event 2 ⋮				

Statistical Analysis Plan

Grade 3				
Event 1				
Event 2				
⋮				
Grade 2				
Event 1				
Event 2				
⋮				
Grade 1				
Event 1				
Event 2				
⋮				

*: C113 stands for the third incidence of Event 1 of Grade 4 in body system A that occurs in patient #1 at Center 1.

Statistical Analysis Plan

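### The planned 95% intervals for adverse event rates ignore variation between subjects, so they are too narrow for events that recur more often in some subjects than in others

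*SAP*

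**What the plan says.** Section 14.2.1 of the SAP sets the unit of analysis as a rate per person-time: "For each event, we will analyze its incidence rate per 100 person-days". The model is "Suppose for each subject, the incidence of a particular event is a Poisson process with the homogeneous incidence rate" λ. Exposure runs from the start of induction: "if a subject is only followed r days after the initiation of induction immunosuppression", the count has mean rλ/100. One estimate is taken over everyone; the "incidence rate will be obtained based on data collected from the available subjects at the analysis time". On the interval: "The 95% confidence interval derived using the maximum likelihood estimator theory will be also reported". The results go into Appendix 4, by body system, grade and event, separately for related and unrelated events.

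Appendix 5 makes clear that repeats are counted. Its footnote explains that "C113 stands for the third incidence of Event 1 of Grade 4 in body system A" for one patient at one center. The same appendix has a column headed "Number and percentage of patients who have had the incidence", with no interval.

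For adverse event rates the SAP plans no robust variance, negative binomial or frailty model, and no check for overdispersion.

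**The concern.** The trial samples subjects, 24 of them, but the planned variance is that of independent events. It is correct only if every subject has the same underlying rate. Several of the targeted events in section 14.2, such as infections, cytopenias, gastrointestinal toxicity and oral ulcers, can occur more than once in a subject over follow-up that runs to 36 months after the last transplant. If some subjects are more prone to an event than others, repeat events carry less information than the model assumes, and the interval is too narrow. The upper limit on a harm rate is then too low too often. The point estimate, events divided by person-days, is not affected.

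This is separate from whether the hazard is constant over time and from how the limits behave at zero or very few events. It does not go away as events accumulate: for a given φ it gets worse as the mean count rises.

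**Working it through.** The SAP states no adverse event rate or interval, so there is no figure of its own to reproduce.

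**Inputs from the SAP.** Number of subjects n = 24 (section 2.1). A single λ, one pooled maximum likelihood estimate and a 95% likelihood interval (section 14.2.1). Repeats counted (Appendix 5).

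**Assumptions, not in the SAP.** Equal follow-up. Subject rates that vary as a gamma distribution with mean 1 and variance φ (the frailty variance), with φ from 0 to 2. Mean events per subject μ from 0.25 to 4.

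**Formula.** Under the planned model the variance of the total count is nμ. With between-subject variation, each subject's count has variance μ + φμ², so the total has variance nμ(1+μφ). The ratio of true to planned standard error is therefore √(1+μφ). For example:

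- μ = 0.25, φ = 1: √1.25 = 1.12
- μ = 1, φ = 1: √2 = 1.41
- μ = 2, φ = 1: √3 = 1.73
- μ = 4, φ = 1: √5 = 2.24

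**Simulated coverage of the planned nominal 95% interval** (40,000 replicates per cell, n = 24). The SAP does not say on which scale the likelihood interval is built, so both are shown (Wald / log scale):

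| Events per subject | φ = 0 | φ = 0.5 | φ = 1 | φ = 2 |
|---|---|---|---|---|
| 0.25 | 93.4 / 95.5 | 92.2 / 94.4 | 90.7 / 93.3 | 87.8 / 91.1 |
| 0.5 | 94.2 / 95.6 | 91.4 / 93.1 | 88.0 / 90.6 | 82.8 / 86.3 |
| 1 | 93.0 / 94.8 | 86.5 / 88.9 | 81.0 / 83.8 | 71.7 / 75.0 |
| 2 | 94.1 / 94.9 | 82.0 / 83.4 | 72.6 / 74.4 | 60.0 / 61.8 |
| 4 | 94.9 / 95.4 | 74.3 / 75.1 | 61.8 / 62.6 | 48.6 / 49.5 |

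With no heterogeneity the planned interval is about right. At 0.25 events per subject (24 × 0.25 = 6 expected events) the log-scale interval loses about 1 to 4 points. At 2 per subject (48 expected events) it loses about 11 to 33.

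**Direction of the error.** At μ = 2 and φ = 1, the Wald upper limit falls below the true rate in about 17% of replicates, against about 4% without heterogeneity.

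**Coverage of the remedy.** A log-scale interval with subject-level robust variance and t limits on 23 degrees of freedom covers, for φ = 0 / 0.5 / 1 / 2:

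- μ = 0.5: 95.8 / 95.4 / 94.6 / 94.1%
- μ = 2: 95.0 / 94.6 / 94.1 / 93.0%
- μ = 4: 95.0 / 94.5 / 94.0 / 93.1%

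The scale matters. The same robust variance on the natural scale covers only about 91% to 92% at φ = 1, and about 90% at φ = 2.

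**The case against.** A reader might take Appendix 5 as evidence that events cluster, because its entry "C111 C112 C113* C221 C231 C232 C331 C421 C461" gives subject counts of 3, 1, 2, 1, 1 and 1. It is not evidence. The codes are dummy entries that explain the labelling, and the accompanying 6 (12.5%) implies 6/0.125 = 48 patients, not 24. Even taken at face value with 24 subjects, the variance-to-mean ratio is 1.58, and allocating 9 events at random to 24 subjects gives a ratio at least that large in about 6.5% of draws. The template shows that repeats are counted, and no more.

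The large coverage losses rest on assumed values of μ and φ, since the SAP contains neither. Appendix 4 is also finely divided, so many cells will hold few events. A cell with 2 to 4 events per subject needs 48 to 96 occurrences of one event at one grade and attribution. This stands: in sparse cells the loss is a few points.

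A reader might also infer that these limits decide whether harm outweighs benefit. The SAP does not say so. No test or stopping rule in it uses them, it does not rank Appendix 4 as the main safety output, and Appendix 5 would show concentration in a few patients, though without an interval.

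Finally, the word homogeneous in section 14.2.1 most naturally means constant over time. The SAP does not say outright that all subjects share one rate. That is implied, because λ has no subject index and one estimate is pooled over subjects. The interval depends on that implication all the same.

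**Conclusion.** The concern holds for adverse events that recur and differ in frequency between subjects. For these, the planned interval is too narrow by a factor of about √(1+μφ). With 24 subjects, equal follow-up and an assumed φ of 0.5 to 2, Wald coverage is about 92% to 88% at 0.25 events per subject, 91% to 83% at 0.5, 87% to 72% at 1 and 82% to 60% at 2. For rare events, or if subjects truly share one rate, little or nothing is lost.

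The documents do not show that clustering is present or how strong it is, and they do not tie any decision to these limits. The defect is overstated precision in a descriptive safety table. It should be corrected because the correction is cheap and the error makes harm rates look better determined than they are.

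**What to change.** In section 14.2.1 and Appendix 4:

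- Keep the point estimate: events divided by person-days, times 100.
- Replace the likelihood interval with one from a log-link Poisson model that has log person-days as offset and subject-clustered robust variance, with t limits on (number of subjects − 1) degrees of freedom.
- Fix in advance when it applies, for example from a minimum total event count, with exact Poisson limits below that count. Do not choose between the two by whether a repeat happened to be observed.
- State that λ is an average rate over subjects, not a rate common to all.

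The cost is SAP wording and a standard software option. No new data are needed, because Appendix 5 already identifies each incidence by patient. Intervals for recurrent events become wider, by roughly √(1+μφ) and slightly more from the t limits. With 24 subjects, coverage can still fall a little short of 95% when heterogeneity is strong (about 93% at φ = 2 with 2 or more events per subject).
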